9.4.2 Exclusion Criteria

If any of the following apply, the subject **MUST NOT** enter the study:

1. Received prior treatment for MDS with lenalidomide or HMAs.
2. History of one of the following myeloproliferative neoplasms: essential thrombocythemia, polycythemia vera, and primary myelofibrosis.
3. Second malignancy currently requiring active therapy (except for hormonal/anti-hormonal treatment, eg, prostate or breast cancer).
4. Central nervous system leukemia based on imaging or documented positive cytology in cerebral spinal fluid.
5. Any uncontrolled grade 3 or higher (per National Cancer Institute [NCI; US] Common Terminology Criteria for Adverse Events [CTCAE], Version 4.03) viral, bacterial, or fungal infection within 14 days prior to the first dose of study treatment. Antimicrobial prophylaxis or ongoing treatment of resolving/controlled infection is permitted.
6. Known to be positive for hepatitis B by surface antigen expression. Known to have active hepatitis C infection (positive by polymerase chain reaction or on antiviral therapy for hepatitis C within the last 6 months).
7. Known to be positive for human immunodeficiency virus (HIV).
8. Documented history of a cerebral vascular event (stroke or transient ischemic attack), unstable angina, or myocardial infarction within 6 months prior to their first dose of study drug, or refractory congestive heart failure unresponsive to medical treatment.
9. Therapy with the following agents within the specified timeframe prior to first study treatment:
 - a. systemic anti-neoplastic or investigational agents within prior 14 days.

- b. hematopoietic growth factors within 7 days (erythropoietin, granulocyte colony stimulating factor, granulocyte-macrophage colony stimulating factor, or thrombopoietin receptor agonists).
10. Known hypersensitivity to any excipient contained in the drug formulation of any study treatment.
11. Prior allo-HCT, for any indication.
12. Hypocellular MDS, defined as bone marrow cellularity <30% in subjects ≤60 years old or <20% cellularity in subjects >60 years old.
13. Candidates for allogeneic stem cell transplant at the time of screening.
14. History of clinically significant liver disease (e.g. liver cirrhosis) or ongoing alcohol abuse.

9.4.3 Withdrawal and Replacement of Subjects

In accordance with the Declaration of Helsinki ([Appendix 18.1](#)) and applicable regulations, a subject has the right to discontinue treatment or withdraw from the study at any time and for any reason without prejudice to his or her future medical care by the physician or at the institution.

9.4.3.1 Discontinuation of Study Drug

Subjects may continue on study treatment until disease progression, relapse, or unacceptable toxicity. After discontinuation of study treatment, subjects who have not experienced progression or relapse will continue to be assessed for response every 4 months through 24 months after EOT or until initiation of another anticancer treatment, progression, or relapse, whichever comes first. All subjects will be contacted for survival status every 2 months after EOT in follow-up until death or study closure, whichever comes first.

A subject's treatment with study drug may be discontinued for any of the following reasons:

- Progressive disease (PD) or relapse after remission
- AE
- Investigator decision
- Subject decision, non-AE
- Study termination by Sponsor
- Other, non-AE

The reason for treatment discontinuation will be recorded in the clinical records and the electronic Case Report Form (eCRF). All subjects who discontinue treatment will undergo an EOT visit (see [Section 10.3](#)). These subjects will continue to be followed for survival and disease status (see [Section 10.4](#)) unless they withdraw from the study (see [Section 9.4.3.2](#)). For replacement of withdrawn/discontinued subjects, see [Section 9.4.3.3](#).

9.4.3.2 Subject Withdrawal From Study

Any subject may be discontinued from the study for any of the following reasons:

- Subject withdrawal of consent
- Study termination by Sponsor
- Lost to follow-up
- Death
- Other

Subjects who withdraw from the study will not be further contacted.

9.4.3.3 Replacement of Subjects

During the Phase 1 Portion, sufficient DLT-evaluable subjects will be enrolled in each cohort for determination of the DLT (6 DLT-evaluable subjects per cohort in the absence of DLTs). During the Phase 2 Portion, subjects who discontinue from treatment or the study will not be replaced.

9.5 Treatment

9.5.1 Treatments Administered

The Investigator must ensure that the investigational product will be used only in accordance with the protocol.

Phase 1 Portion

During the Phase 1 Portion of the study, vadastuximab talirine (SGN-CD33A) will be administered every 4 weeks (after azacitidine on the last day of azacitidine administration) via IV push at the assigned dose level (3 to 20 mcg/kg), based on the dose evaluation cohort.

Subjects will also receive azacitidine 75 mg/m² SC or IV (at the Investigator's discretion) for 7 days (7 consecutive days or 5 days on/2 days off/2 days on), beginning on Day 1 of repeated 4-week cycles.

Phase 2 Portion

During the Phase 2 Portion of the study, subjects will be randomized to receive either vadastuximab talirine (SGN-CD33A) administered every 4 weeks (after azacitidine on the last day of azacitidine administration) via IV push at the dose determined in the Phase 1 Portion or placebo every 4 weeks (after azacitidine on the last day of azacitidine administration) via IV push.

All subjects will also receive azacitidine 75 mg/m² SC or IV (at the Investigator's discretion) for 7 days (7 consecutive days or 5 days on/2 days off/2 days on), beginning on Day 1 of repeated 4-week cycles.

9.5.1.1 Required Premedication and Postmedication

Subjects receiving azacitidine should be premedicated for the prevention of nausea and vomiting according to institutional practice.

Prophylaxis/treatment of hematologic toxicity and infection may be administered according to institutional practice.

9.5.1.2 Vadastuximab Talirine

Detailed information describing the preparation, administration, and storage of vadastuximab talirine is located in the Pharmacy Binder.

9.5.1.2.1 Description

Vadastuximab talirine is a sterile, preservative-free, lyophilized cake or powder, supplied in single-use amber vials. See the Pharmacy Binder for further information.

9.5.1.2.2 Method of Procurement

Vadastuximab talirine and matching placebo will be provided by the Sponsor.

9.5.1.2.3 Dose and Administration

Administration of SGN-CD33A will be via IV push. It is recommended that SGN-CD33A be administered via central venous access port (eg, peripherally-inserted central catheter [PICC], Hickman line, or similar according to institutional standard). However, if SGN-CD33A is not administered via central venous access port, a secure and free-flowing peripheral line must be used. Due to potential for severe tissue damage, monitor the injection site closely for redness, swelling, pain, infection during and at any time after administration. Advise patients to report redness or discomfort promptly at the time of administration or after infusion. Follow institutional guidelines for the administration of chemotherapy and take precautions to prevent extravasation per institutional standards and as described by Schulmeister. [25]

Depending on the lot of study treatment supplied, a sterile 0.2-µm filter may be required for administration; see the Pharmacy Binder for details. After the infusion, the IV infusion line

(including the filter and any associated tubing or closed-delivery injection devices) must be flushed with at least 20 mL of saline.

Vadastuximab talirine will be administered in repeated 4-week cycles after azacitidine on the last day of azacitidine treatment, via IV push.

During the Phase 1 Portion of the study, the dose level will be determined according to the dose-escalation schedule.

During the Phase 2 Portion of the study, the dose level will be the dose level selected by the SMC based on the phase 1 data. Subjects in the Phase 2 Portion of the study will receive either vadastuximab talirine or matching placebo.

Dosing is based on subject weight. Doses will be adjusted for subjects who have a $\geq 10\%$ change in weight from baseline. **An exception to weight-based dosing is made for subjects weighing greater than 100 kg; doses will be based on 100 kg for these individuals.** Refer to the Pharmacy Binder for further details.

9.5.1.2.4 Preparation

Vadastuximab talirine vials are provided via single-use containers. Any partially used vials or diluted dosing solutions should be discarded using appropriate institutional drug disposal procedures.

Vadastuximab talirine drug product is reconstituted with sterile Water for Injection (WFI), United States Pharmacopeia (USP) or equivalent, for IV administration. The reconstituted vadastuximab talirine drug product is a clear to slightly opalescent, colorless to light yellow solution. Depending on the dose level, the reconstituted solution is either used directly, or subsequently diluted in sterile 0.9% Sodium Chloride for Injection, USP or equivalent, for IV administration.

Detailed drug preparation instructions are provided in the Pharmacy Binder.

9.5.1.2.5 Study Treatment Labeling and Packaging

Vadastuximab talirine is the International Nonproprietary Name (INN) assigned to SGN-CD33A. Drug product vials may be labeled as SGN-CD33A or as vadastuximab talirine; the 2 names can be used interchangeably.

9.5.1.2.6 Study Treatment Storage and Accountability

It is forbidden to use investigational drug material for purposes other than as defined in this protocol.

Study Treatment Storage

Vials containing vadastuximab talirine must be stored under refrigeration at 2-8°C, protected from light (both sunlight and artificial light).

The chemical and physical stability of the reconstituted drug product has been demonstrated for 24 hours at 2-8°C, protected from light. However, vadastuximab talirine drug product does not contain preservatives; therefore, from a microbiological standpoint, opened and reconstituted vials should be used immediately. If not used immediately, the in-use storage of the reconstituted product should not be longer than 24 hours under refrigeration at 2-8°C. If dilution is needed, the reconstituted drug product should be diluted in 0.9% Sodium Chloride Injection, USP, or equivalent, at the time of use. The prepared dosing solution (reconstituted drug product or drug product dilution) should be used within 4 hours after exposing to ambient temperature and light conditions.

Study Treatment Accountability

Drug accountability instructions are provided in the Pharmacy Binder.

9.5.1.3 Azacitidine

Azacitidine is marketed in the US as VIDAZA® by Celgene Corporation Summit, NJ USA. Please refer to the approved US prescribing information (USPI) for detailed information.

9.5.1.3.1 Description

Azacitidine is a pyrimidine nucleoside analog of cytidine.

9.5.1.3.2 Method of Procurement

Commercially available azacitidine will be provided by the study sites from their usual suppliers.

9.5.1.3.3 Dose and Administration

The starting dose for the first treatment cycle for all subjects is 75 mg/m² SC or IV (at the Investigator's discretion), 7 days per cycle, either on the first 7 days or 5 days on/2 days off/2 days on.

9.5.1.3.4 Preparation

Azacitidine will be prepared for SC or IV administration according to the USPI and local standard of care.

9.5.1.3.5 Storage and Accountability

Azacitidine must be stored, distributed, and disposed of according to institutional practice and the USPI.

9.5.1.4 Management of Adverse Reactions

9.5.1.4.1 Management of Infusion Reactions

Infusions should be administered at a site properly equipped and staffed to manage anaphylaxis should it occur. All supportive measures consistent with optimal subject care should be given throughout the study according to institutional standards. Supportive measures may include extending the infusion time and/or administering medications for infusion-related reactions.

9.5.1.4.2 Overdose

In the event of an overdose $\geq 10\%$, the site should notify the sponsor as soon as they are aware of the overdose.

9.5.1.4.3 Dose Modifications

Common toxicities including myelosuppression, nausea, gastrointestinal toxicity, fatigue, pyrexia, headache, weight decrease, dyspnea, rash, and stomatitis should be managed according to institutional standards or accepted guidelines (eg, American Society of Clinical Oncology [ASCO] guidelines for the use of WBC growth factors [26]). Growth factor support may be administered as needed according to institutional standard of care.

Vadastuximab Talirine

[Table 2](#) describes guidelines for dose modifications of vadastuximab talirine (Phase 1 Portion) or blinded study treatment (Phase 2 Portion) for toxicity.

Dose delays of any study treatment are permitted. If dosing is delayed for azacitidine, vadastuximab talirine (Phase 1 Portion), or blinded study treatment (Phase 2 Portion), both study treatments should be held and resumed together on the same schedule except when one agent is omitted during a cycle due to toxicity.

For patients who achieve a response to therapy, dose decreases, delays, or dose re-escalation (to original dose level) are permitted at the discretion of the medical monitor and site Investigator. Following achievement of marrow blast clearance to $<5\%$ (ie, a CR or marrow CR), patients originally treated with a dose higher than 5 mcg/kg of study drug will receive azacitidine with vadastuximab talirine (Phase 1 Portion) or blinded study treatment (Phase 2 Portion) as continuation therapy at the maintenance dose of 5 mcg/kg in subsequent cycles.

Azacitidine, vadastuximab talirine (Phase 1 Portion), or blinded study drug (Phase 2 Portion) may be permanently discontinued in the event of unacceptable related toxicity. Subjects will not be considered off study treatment until both study treatments are discontinued.

If subjects become candidates for stem cell transplant after enrollment, vadastuximab talirine must be discontinued at least 30 days prior to initiation of preparative regimen for stem cell transplant.

Table 2: Dose Modifications for Vadastuximab Talirine-Associated Toxicity

Category	Event	Action
Hematologic toxicity with marrow blast count <5% ^a	≥ Grade 3 neutropenia or thrombocytopenia	Cycles of treatment may be delayed up to 14 days ^b until hematologic recovery is observed. Adequate hematologic recovery is defined as neutropenia and thrombocytopenia improved to < grade 3 (unsupported), OR ANC / platelets ≥ [(NADIR COUNT ^c) + (BASELINE COUNT ^d – NADIR COUNT) x 0.50] If hematologic recovery as defined above has not occurred within 14 days of the end of the cycle (by Day 42), omit vadastuximab talirine (Phase 1) or blinded study treatment (Phase 2) from the next cycle, and initiate next dose of azacitidine based on marrow cellularity as defined in Table 3.
Hematologic toxicity with marrow blasts ≥5% ^b	≥ Grade 3 neutropenia or thrombocytopenia	Treatment may continue without dose modification.
Clinically significant non-hematologic toxicity or asymptomatic non-hematologic laboratory abnormality (with the exception of hepatic toxicity)	≥ Grade 3 event	Treatment delay of up to 14 days is permitted until resolution of toxicity to < grade 3.
Laboratory evidence of hepatic toxicity (elevation in ALT, AST, or total bilirubin)	≥ Grade 3 event	Treatment delay of up to 14 days is required until resolution of toxicity to ≤ grade 1 or baseline. If toxicity has not resolved within 14 days, permanently discontinue vadastuximab talirine (Phase 1) or blinded study treatment (Phase 2)

ALT = alanine aminotransferase; ANC = absolute neutrophil count; AST = aspartate aminotransferase.

- a If cytopenias above grade 3 (e.g., ANC <1000/mm³ or platelets <50 x 10⁹/L) are present at Day 28 of a cycle in which no response assessment is required, an ‘unscheduled’ bone marrow biopsy is required within 14 days of the scheduled end of the cycle (eg, between Day 28 and Day 42). If the bone marrow cellularity is ≤10%, vadastuximab talirine or blinded study treatment will be permanently discontinued. If marrow cellularity is >10%, follow guidance as above.
- b Delays of >14 days may be permitted with approval of the medical monitor.
- c Nadir Count = the lowest count reached during the treatment cycle.
- d Baseline Count = counts prior to Cycle 1 of study treatment.

Azacitidine

Dose modifications to azacitidine, including permanent discontinuation due to toxicity, are at the discretion of the treating physician and should adhere to the USPI, the summary of product characteristics (SMPC), or institutional guidelines/standards. Recommended schedule modifications for azacitidine in patients with delayed count recovery and <5% blasts are provided in Table 3.

Table 3: Recommended Scheduled Modifications for Azacitidine in Patients with <5% Blasts and Incomplete Hematologic Recovery at Day 42^a

Bone Marrow Cellularity:	>30%	15-30%	<15%
Timing of Next Cycle	Next cycle may begin	Delay next cycle until ANC and platelets \geq [(NADIR COUNT) + (BASELINE COUNT – NADIR COUNT) x 0.50]	Delay next cycle until ANC and platelets \geq [(NADIR COUNT) + (BASELINE COUNT – NADIR COUNT) x 0.75]

a If vadastuximab talirine (Phase 1) or blinded study drug (Phase 2) was omitted during the previous cycle, consider dose reduction of azacitidine to 50% upon initiation of next cycle.

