Azacitidine will be given on 7 days per cycle, either on the first 7 days or 5 days on/2 days off/2 days on; vadastuximab talirine will be given after azacitidine on the last day of azacitidine administration in each cycle. Response assessments (bone marrow examination and complete blood count [CBC]) will be conducted on Day 22-29 of even-numbered cycles until CR, then every 4 cycles thereafter. Subjects may continue on study treatment until disease progression, relapse, or unacceptable toxicity. After discontinuation of study treatment, subjects who have not experienced progression or relapse will continue to be assessed for response every 4 months through 24 months after the end of treatment (EOT) or until initiation of another anticancer treatment, progression, or relapse, whichever comes first. All subjects will be contacted for survival status every 2 months after EOT in follow-up until death or study closure, whichever comes first. Safety will be monitored through the surveillance of AEs, laboratory test measures, physical examination findings, and concomitant medication records. An additional bone marrow examination will be conducted for research purposes for subjects in the Phase 1 Portion of the study only.

After 6 DLT-evaluable subjects have had the opportunity to complete at least Cycle 1 (Cycle 1 of treatment is completed when the patient receives the first dose of azacitidine on Day 1 of Cycle 2) of treatment in each planned dose cohort, the data will be aggregated and analyzed by an SMC (Section 13.6.9). Based on the evaluation of the data, including the incidence of DLT in each cohort, the SMC may recommend the dose of vadastuximab talirine for the Phase 2 Portion of the study at the time of the evaluation. If additional safety information is required to recommend a phase 2 dose, the SMC could recommend enrollment of up to 12 additional treated subjects to continue to evaluate the safety of the combination at vadastuximab talirine dose(s) of 3, 5, 10, or 20 mcg/kg. Subsequently, upon completion of dose escalation, up to 12 more expansion patients may be enrolled (maximum of 24 expansion patients total), at any dose level not previously shown to exceed the MTD, to further characterize safety, PK, and activity.

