 - Whole blood (MDSC and CD33 expression; [Section 11.4](#))
 - 192 hours (± 4 hours) after the end of the vadastuximab talirine infusion (Day 10 or 12)
- Day 28 (± 7 days):
 - Bone marrow biopsy to assess bone marrow cellularity. Cycle 1 marrow biopsy may be omitted if either a) patient has recovered counts to less than grade 3 cytopenias, ie, absolute neutrophil count (ANC) $>1000/\text{mcL}$ AND platelet count $>50,000/\text{mcL}$, without transfusion support, by Day 28 of Cycle 1 or b) there is evidence in the peripheral blood of active MDS, eg, circulating blasts.

Note:

- A. If the marrow is not hypocellular (total marrow cellularity $\geq 10\%$), the patient may proceed to Cycle 2 per dose modification guidance, depending on marrow blast percentage / remission status.*
- B. If the marrow is hypocellular (total marrow cellularity $< 10\%$), Cycle 2 should be delayed until count recovery (defined in Cycle 1 as thrombocytopenia and neutropenia improving to less than CTCAE grade 4, or by the following formula: $[(\text{NADIR COUNT}) + (\text{BASELINE COUNT} - \text{NADIR COUNT}) \times 0.75]$. If neutrophil count or platelet count have not recovered to less than Grade 4 by Day 42, a repeat marrow should be performed within a week. If the marrow is hypocellular at Day 42, then the subject will have experienced a DLT (posttreatment grade 4 neutropenia or grade 4 thrombocytopenia lasting > 42 days from the start of therapy in the absence of evidence of active MDS); if marrow cellularity has recovered to $\geq 10\%$, and ongoing cytopenia(s) are attributed to active MDS, then Cycle 2 may be initiated.*

10.2.1.2 Cycle 2

- Day 1 (± 1 day), pretreatment:
 - Biomarker assessments (Section 11.4)
 - Whole blood (sCD33 - cytokines and research; MDSC; CD33 expression; and PBMCs)
 - ECOG performance status and weight (Section 11.5)
 - PRO questionnaire (Section 11.9)
 - Clinical laboratory tests (CBC with differential, serum chemistry including ferritin, and urinalysis; Section 11.7)
 - Blood samples for ATAs (within 24 hours before beginning the azacitidine infusion; Section 11.8)
- Days 1 to 6 (if azacitidine is administered on 7 consecutive days) or Days 1 to 5, and 8 (if administered 5 days on/2 days off/2 days on): Administer azacitidine according to the selected treatment schedule (Section 9.5.1.3)
- Day 7 (if azacitidine is administered on 7 consecutive days) or Day 9 (if administered 5 days on/2 days off/2 days on), pretreatment:

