11.3 Bone Marrow Examination

Bone marrow examinations for disease assessment at baseline, on treatment, and during follow-up will be performed according to local standards and recorded on the eCRF. After EOT, bone marrow examinations for disease assessment should be performed every 4 months through 24 months after EOT or until initiation of another anticancer treatment, progression, or relapse. Bone marrow examination should be based on a bone marrow biopsy; however, if marrow cannot be biopsied, but aspiration is successful, the aspirate may be used to determine blast count.

In addition to response assessment time points, a bone marrow biopsy will be performed between Day 28 and Day 42 of any cycle in which the patient has not achieved hematologic recovery (as defined in Table 2). This biopsy is to determine the blast count and marrow cellularity, in order to determine if dose modification / dose delay is required in the subsequent cycle (Table 2 and Table 3). This biopsy to assess cellularity is not required if counts have recovered (ie, ANC >1000/mm³ AND platelet count >50,000/mm³, without transfusion support, by Day 28 of the cycle) or if there are circulating blasts in the peripheral blood (as evidence of active MDS).

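### Phase 1, Cycle 1: with marrow blasts below 5% and cellularity below 10%, Table 2 permanently stops vadastuximab talirine while Section 10.2.1.1 only delays Cycle 2

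*Protocol*

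**What the plan says.** Protocol Section 9.5.1.4.3, Table 2, footnote a, is attached to the row for hematologic toxicity with marrow blasts below 5%. It concerns cytopenias (ANC below 1000/mm³ or platelets below 50 x 10⁹/L) that "are present at Day 28 of a cycle in which no response assessment is required, an ‘unscheduled’ bone marrow biopsy is required". The consequence at low cellularity is: "If the bone marrow cellularity is ≤10%, vadastuximab talirine or blinded study treatment will be permanently discontinued". Otherwise: "If marrow cellularity is >10%, follow guidance as above". The same row of Table 2 states: "Adequate hematologic recovery is defined as neutropenia and thrombocytopenia improved to < grade 3 (unsupported", or alternatively counts at or above nadir + 0.50 x (baseline − nadir). For blasts of 5% or more, Table 2 lets treatment go on unmodified.

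Section 10.2.1.1 (Phase 1, Cycle 1) schedules a marrow biopsy at Day 28 ± 7 days to assess cellularity: "Cycle 1 marrow biopsy may be omitted if either a) patient has recovered counts to less than grade 3 cytopenias", or if the blood shows active MDS. Two notes follow.
- Note A: at 10% or more the marrow is not hypocellular, and the subject may go on to Cycle 2 under the dose modification guidance, depending on blasts and remission status.
- Note B: for a marrow below that level, "Cycle 2 should be delayed until count recovery (defined in Cycle 1 as thrombocytopenia and neutropenia improving to less than CTCAE grade 4"; a formula with a factor of 0.75 is the alternative. If counts are still grade 4 at Day 42, the marrow is repeated. A marrow that is still hypocellular makes the case a DLT. If cellularity is back to 10% or more and the cytopenias are attributed to active MDS, Cycle 2 may start.

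**The concern.** The two texts appear to give one biopsy result two different consequences: the investigational drug is stopped for good under one and the next cycle is merely postponed under the other. Neither refers to the other at this point, and no precedence rule is given. If sites follow different pages, Phase 1 subjects in the same state could be managed differently. That bears on their safety, and on the exposure and tolerability data from which the Phase 2 dose is recommended.

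**Working it through.** No arithmetic figure of the plan is at issue, so the check sets the two rules side by side.

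**Step 1. Does footnote a reach Cycle 1?** Section 9.1.1 says that response assessments "will be conducted on Day 22-29 of even-numbered cycles until CR, then every 4 cycles thereafter". Cycle 1 is odd-numbered and has none, so it meets the footnote's condition. Section 11.3 agrees: "a bone marrow biopsy will be performed between Day 28 and Day 42 of any cycle in which the patient has not achieved hematologic recovery". That section sends the result to Tables 2 and 3. Nothing exempts Cycle 1.

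**Step 2. Do both rules reach the same subject?** The count triggers agree: ANC 1000 and platelets 50,000 in both places. The biopsy windows are Day 28 to 42 (footnote a) and Day 21 to 35 (28 ± 7, Section 10.2.1.1). They overlap from Day 28 to Day 35. Take a Phase 1 subject in Cycle 1 with such cytopenias, a biopsy in that overlap and no circulating blasts.

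**Step 3. Compare the instructions.**

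| Marrow result | Table 2 | Section 10.2.1.1 | Outcome |
|---|---|---|---|
| Blasts <5%, cellularity <10% | Vadastuximab talirine stopped permanently | Note B: Cycle 2 delayed until recovery; discontinuation not mentioned | Unreconciled |
| Blasts <5%, cellularity exactly 10% | Stopped permanently (cut-off ≤10%) | Note A: not hypocellular; Cycle 2 under the dose modification guidance | Boundary inconsistency |
| Blasts <5%, cellularity >10% | Table's delay/omit guidance | Note A: dose modification guidance | Agree |
| Blasts ≥5%, cellularity <10% | Treatment may continue unmodified | Note B, not limited by blast count: delay | Second mismatch |

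**Step 4. Compare the recovery definitions.** SAP Appendix 3 gives the grade limits: for neutrophils, grade 3 is 500 to below 1000/mm³ and grade 4 is below 500; for platelets, grade 3 is 25,000 to below 50,000/mm³ and grade 4 is below 25,000. A subject whose counts have risen only into the grade 3 range has therefore recovered under Note B. Under Table 2 that subject has not recovered by grade, and could qualify only through the 0.50 formula.

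The formulas need separate treatment. The 0.75 target exceeds the 0.50 target by 0.25 x (baseline − nadir). However, Table 3 also uses 0.75 when cellularity is below 15%, so Note B's formula agrees with Table 3. What has no counterpart in Table 2 or Table 3 is Note B's acceptance of recovery to less than grade 4.

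**The case against.** The strongest reply is that stopping one drug and delaying a cycle are compatible. Footnote a concerns only vadastuximab talirine or blinded drug; Note B concerns when Cycle 2 starts. Section 9.5.1.4.3 allows one agent to be omitted or permanently discontinued while the other continues, and completion of Cycle 1 is defined by azacitidine alone. A site could stop vadastuximab talirine and delay azacitidine, and so comply with both. A second reply is that the Cycle 1 biopsy is scheduled in Section 10.2.1.1 and therefore lies outside a footnote about unscheduled biopsies.

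Both readings are possible, but neither is written. Section 9.1.1 places vadastuximab talirine in every cycle, and Section 9.5.1.4.3 has delayed treatments resume together unless one is omitted for toxicity, so a delayed Cycle 2 includes it by default. Section 11.3 extends the cellularity biopsy to any cycle, which counts against the second reading. Even the first reading leaves the grade 3 versus grade 4 recovery mismatch.

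Three parts of the opposing case stand, and each rules out a stronger claim that a reader might infer.
- **Opposite instructions at exactly 10%.** Note A refers to the dose modification guidance, which includes Table 2. The label differs, but this is not a flat contradiction.
- **Every Phase 1 subject with low cellularity is affected.** Footnote a belongs to the row for blasts below 5%, whereas inclusion criterion 1 requires at least 5% at entry. The direct clash therefore needs blast clearance during Cycle 1. The biopsy may also be skipped when circulating blasts are present.
- **One subject handled differently could tip a cohort of 6, where 2 DLTs decide.** The hematologic DLT rests on grade 4 cytopenia beyond 42 days without active MDS. It does not depend on Table 2 or on whether vadastuximab talirine continues. Note B holds Cycle 2 until recovery or the Day 42 reassessment, and a subject who stops for an AE stays DLT-evaluable. No path to a changed DLT count is shown.

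**Conclusion.** The point holds in a limited form. In Phase 1, a Cycle 1 subject with Day 28 cytopenias, marrow blasts below 5% and cellularity below 10% falls under two current rules with different consequences for vadastuximab talirine, and the protocol does not say which governs. The boundary, the less-than-grade-4 recovery criterion and the handling of blasts of 5% or more are related, lesser mismatches.

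The consequence is possible inconsistent stopping or re-exposure of identical subjects, which matters for safety and for Phase 1 exposure data. Its frequency cannot be estimated, because the documents give no rate of Cycle 1 blast clearance with a hypocellular marrow. The clash does not extend to Phase 2: Section 10.2.2.1 has no Day 28 marrow rule for Cycle 1, so Table 2 stands alone there.

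The conclusion assumes that footnote a means what it says about cycles without a response assessment, and that no document outside the protocol and SAP, such as a study manual, settles the order of precedence.

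**What to change.** Reconcile Table 2 (including footnote a), Table 3 and Notes A and B of Section 10.2.1.1, or state explicitly which of them governs the Phase 1 Cycle 1 biopsy. The result should give:
- one cellularity boundary, written the same way throughout;
- one stated consequence for vadastuximab talirine, kept distinct from the timing of azacitidine;
- one count-recovery definition for Cycle 1, or an express Cycle 1 exception in Table 2;
- a statement of whether Note B depends on blast percentage.

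The choice of rule is for the clinical team; none is proposed here. The cost is protocol amendment wording and notice to sites, with no added procedures.
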